5.6.2 Secondary Efficacy Analyses

The secondary endpoints will be summarized with descriptive statistics in accordance with Section 5.3 for the Efficacy Evaluable Population.

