6.1 Duration of Patient Participation

The anticipated duration of participation for the screening and treatment periods, for each patient, is determined by the following:

Screening may not exceed 28 days before the first dose of study drug. In the absence of treatment delays due to AE(s), treatment may continue until one of the following criteria applies:

1. Confirmed disease progression (refer to [Section 9.1.2](#) and [Section 9.1.5](#)),
2. Intercurrent illness or unacceptable AE(s) that prevents further administration of treatment,
3. Patient decides to withdraw from the study, or
4. General or specific changes in the patient's condition render the patient unacceptable for further treatment in the judgment of the Investigator.

Patients will be allowed to remain on active treatment for 35 treatment cycles or until documented progressive disease (PD) or unacceptable toxicity. All patients will be followed for survival.

Patients will be followed for survival until death, withdrawal of consent, or study closure, whichever occurs first. Patients removed from study treatment for unacceptable AE(s) should be followed until resolution or stabilization of the AE, and should be followed for disease progression and or initiation of a new therapy and survival where feasible.

In addition, the study may be terminated by the study Sponsor; in this case all efforts will be made to continue to provide study drug to patients who are continuing to benefit clinically from them. However, this cannot be guaranteed.

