4.2.1.3 Exploratory Efficacy Variable

Tumor response and progression evaluated using iRECIST.

- a) iBOR
- b) Duration of iBOR
- c) Time to iCPD

Efficacy, as defined by the ORR, will be assessed through RECIST v 1.1 until response or progression and will be subsequently analyzed through iRECIST (iCR, or iPR or iSD or after iUPD iCR, iPR or iSD or iCPD). iBOR will also be assessed.

Overall survival will also be assessed.

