4.2.2.2 Secondary Efficacy Endpoints

Clinical Activity: Tumor response will be assessed in all four cohorts by monitoring:

- Progression Free Survival (PFS)
- Clinical Benefit Rate (CBR) defined as CR+PR+SD
- Time to response
- Duration of response
- Overall Survival (OS)

Measures of tumor response will be evaluated using RECIST v1.1 until response or progression and will be subsequently analyzed through iRECIST as an exploratory endpoint (see below).

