4.2.3.6 Overall Survival (OS)

Overall survival (OS) is defined as the time from the first dose of study treatment to the date of death due to any cause. For patients who do not die, the OS time will be censored on the date when the patient was last known to be alive. The date “last known to be alive” will be defined as the latest date of contact with the patient based on all collected evaluation dates, including the telephone contacts for the survival follow-up.

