5.2.2 Efficacy Evaluable Population

Will comprise all patients in the ITT population who have baseline and at least one post-baseline efficacy assessment, unless the patient dies or experiences an AE that results in study drug termination prior to assessment. At that point, the patient will be considered to have progressed in the absence of other data.

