5.6.3 Exploratory Efficacy Analyses

The exploratory endpoints will be summarized with descriptive statistics in accordance with Section 5.3 for the Efficacy Evaluable Population.

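### Overall survival is summarised on the Efficacy Evaluable Population, where a patient with no post-baseline assessment is included only after death or an AE-related stop, so the reported median may be biased

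*SAP*

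**What the plan says.** SAP section 4.2.2.2 lists OS among the secondary endpoints for all four expansion cohorts, and section 5.6.2 gives the population: "The secondary endpoints will be summarized with descriptive statistics in accordance with Section 5.3 for the Efficacy Evaluable Population". In the escalation phase OS appears under the exploratory variables (SAP section 4.2.1.3: "Overall survival will also be assessed"), and section 5.6.3 assigns the same set: "The exploratory endpoints will be summarized with descriptive statistics in accordance with Section 5.3 for the Efficacy Evaluable Population". Neither section makes an exception for OS.

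SAP section 5.2.2 builds the set from ITT patients "who have baseline and at least one post-baseline efficacy assessment". The requirement is waived in two cases, which the same sentence words as follows: "unless the patient dies or experiences an AE that results in study drug termination prior to assessment". Patients covered by that exception count as progressed when there are no other data. Protocol section 12.4 has the same rule.

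OS itself is defined in SAP section 4.2.3.6 from first dose to death from any cause, censored at last contact, "including the telephone contacts for the survival follow-up". Protocol section 6.1 says "All patients will be followed for survival", ending at death, withdrawal of consent or study closure, and section 6.3 sets the contacts at every 3 months.

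SAP section 5.2.1 defines a wider set, ITT, which is also the safety population. No section assigns OS to it. The one planned sensitivity analysis (section 5.6.5) concerns the primary endpoint and removes patients.

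**The concern.** A requirement for a post-baseline assessment makes sense for tumour response. OS needs no tumour assessment, so here the requirement discards usable follow-up. The exception also makes membership of the set depend on death, which is the OS event.

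The patients concerned are plausible. The first tumour measurement is at week 9 (SAP section 4.2.3). Protocol section 4.3 lets the investigator withdraw a patient whose condition has changed, and section 8.1 says that progression of the cancer under study is not an adverse event. A patient who stops for clinical deterioration before week 9, is not scanned and is alive at that point is therefore not an AE stop. Whether that patient's later death counts in the OS analysis depends on how section 5.2.2 is read.

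At stake are the Kaplan-Meier plot, the median and its 95% interval (SAP section 5.3) in single-arm cohorts of 26 to 30 patients, where leaving out two or three patients can be visible.

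**Working it through.** Neither document gives a sample size, event count or expected value for OS, so there is no planned figure to reproduce. The share of unassessed patients and their prognosis are not documented either. All inputs marked as assumed below are illustrative.

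**Two readings of section 5.2.2 for a patient with no assessment**
- Reading A: kept if death occurs before the planned week-9 assessment.
- Reading B: kept if death is observed at any time without an assessment.

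Under both, an unassessed patient who stays alive and had no AE stop is left out.

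**Simulation.** Assumed: 27 patients, exponential survival, median OS 9 months if assessed, follow-up uniform from 9 to 24 months, early death meaning within 2.1 months, 4000 cohorts per setting. Unassessed patients have median OS 2 months (deterioration) or 12 months (withdrawal with better prognosis). Shift in median OS, evaluable set minus all patients, in months:

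| Setting | 5-10% unassessed | 20% unassessed |
|---|---|---|
| Deterioration, reading A | +0.1 to +0.3 | about +0.7 (6.7 to 7.4) |
| Deterioration, reading B | about 0 | about 0 (6.7 to 6.6) |
| Withdrawal, either reading | -0.4 to -0.7 | about -1.0 (9.5 to 8.4-8.5) |

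**Large-sample check of reading A.** Let f be the unassessed share and m their median OS. The median in all patients solves (1-f)·2^(-t/9) + f·2^(-t/m) = 0.5. On the evaluable set, beyond 2.1 months, it solves (1-f)·2^(-t/9) / [(1-f) + f·q] = 0.5, where q = 1 - 2^(-2.1/m).
- f = 0.20, m = 2: all patients 6.63. q = 1 - 2^(-1.05) = 0.517; 2^(-t/9) = 0.5 × 0.9034/0.8 = 0.5646; t = 7.42. Shift +0.8.
- f = 0.10, m = 2: all patients 7.81; 2^(-t/9) = 0.5 × 0.9517/0.9 = 0.5287; t = 8.27. Shift +0.5.
- f = 0.20, m = 12: all patients 9.51. q = 1 - 2^(-0.175) = 0.114; 2^(-t/9) = 0.5 × 0.8228/0.8 = 0.5143; t = 8.63. Shift -0.9.
- f = 0.10, m = 12: all patients 9.25; 2^(-t/9) = 0.5 × 0.9114/0.9 = 0.5063; t = 8.84. Shift -0.4.

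The signs agree with the simulation. The sizes differ by 0.1 to 0.3 months, so the shifts should be read to no better than a few tenths of a month at this cohort size.

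**Why reading B gives no shift under deterioration.** The average chance of still being alive at the end of follow-up is (m/ln 2)·[2^(-9/m) - 2^(-24/m)]/15. For m = 2 this is 2.885 × (0.0442 - 0.0002)/15 = 0.008, so about 99% of these patients die under observation and are kept. For m = 12 it is 17.31 × (0.5946 - 0.25)/15 = 0.40, so about 40% are dropped, all of them alive.

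**Equal prognosis, using medians quoted in the protocol.** Take 7 months (section 1.5.3, cervical) and 13.1 months (section 1.5.2, ovarian) with exponential survival. Week 9 is 63/30.4375 = 2.07 months. For a 7-month median, S9 = 2^(-2.07/7) = 0.815. Suppose a share d = 10% of those alive at week 9 is left out (assumed) while early deaths stay in.
- Week-9 survival on the evaluable set: 0.815 × 0.9/(1 - 0.1 × 0.815) = 0.798.
- Median: 7.0 becomes 6.8 months; for 13.1 months it becomes 12.9.
- Patients lost: 26 × 0.815 × 0.1 = about 2 of 26.

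If the excluded patients instead have twice the hazard after week 9, the sign reverses: 6.6 in all patients against 6.8 on the evaluable set, and 12.3 against 12.9.

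**The case against.** The strongest reply is that the effect is small and unproven. Only unassessed patients matter, and the protocol works to keep them few: section 6.3.2 schedules radiological assessment for patients who stop without progression, and section 9.1.5 asks for continued imaging. Nothing in the documents supports a share of 20%. In the simulated deterioration setting at 20%, the 90% sampling range of the all-patient median is about 3.7 to 11.1 months, far wider than the shift. SAP section 5.4.4 excludes inference on secondary endpoints. All of this stands, and it limits the weight of the point. It gives no reason to select on the outcome when the wider set is already defined.

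The definition refers to an efficacy assessment, not a scan, and protocol section 12.7 mentions clinical response per investigator alongside imaging. If a clinical assessment counted, fewer patients would be excluded. SAP section 4.2.3 defines the response endpoints by tumour measurement, so imaging is the likely intent, but the text does not settle it.

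Four stronger readings are tempting and are not supported:
- A reader might infer that OS is certainly biased. One of the three settings above shows essentially no shift.
- A reader might infer that early deaths are dropped, which would raise the median by about 2.1 months (7.0 to 9.1, or 13.1 to 15.2) if every death before week 9 were unassessed and everyone alive then were assessed. Section 5.2.2 goes on to count such patients as progressed, which has a purpose only if they are in the set.
- A reader might infer that OS data will be complete for everyone treated. Follow-up ends at consent withdrawal, so for those patients a wider set adds only records censored early.
- A reader might infer a planned comparison with published survival. Neither document plans one.

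**Conclusion.** The point holds as a question of population choice. As written, OS in both phases is summarised on a set that an unassessed patient joins only through death or an AE-related stop, although OS needs no assessment and its follow-up is planned for all patients. The Kaplan-Meier median and interval may be biased in either direction. With 5-10% unassessed the shift is a few tenths of a month (about +0.3 to -0.7 at the extremes, and about 0 in one setting); with 20% it runs from about +0.7 to -1.0 months. These sizes rest on assumed shares, assumed prognosis and exponential survival. ORR is the only formally tested endpoint (SAP section 5.6), so no error rate, stopping rule or decision depends on this. The change is worth making because it is cheap and removes this selection, not because a large error has been shown.

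**What to change.** State in SAP sections 5.6.2 and 5.6.3 that OS is analysed on the ITT/safety population of section 5.2.1, with censoring at last contact as in section 4.2.3.6. Changing 5.6.2 alone would leave escalation-phase OS where it is. If the evaluable-set OS is still wanted, report it as supportive.

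Describe the set as patients who received pembrolizumab and birinapant, not as all treated. Section 5.2.1 requires a dose of both drugs, while protocol section 12.1 speaks of either product for safety analyses, so a patient who received only pembrolizumab would still be outside the OS analysis.

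The cost is one sentence in each section and a different population flag for the OS outputs. No new data are needed and the primary analysis is unchanged.

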5.6.3 Exploratory Efficacy Analyses

The exploratory endpoints will be summarized with descriptive statistics in accordance with Section 5.3 for the Efficacy Evaluable Population.

5.6.4 Subgroup Analyses

No pre-defined analysis on subgroups are planned.

5.6.5 Sensitivity Analyses

A sensitivity analysis of the primary endpoint will be conducted if there are patients that are wrongly included into the study and receives a dose of pembrolizumab and birinapant. In that case, the primary efficacy analysis will be repeated when those patients are excluded from the efficacy evaluable population, for the cohorts it concerns, as a sensitivity analysis. Also other major protocol deviations may be considered in this sensitivity analysis.

5.7 *Safety Analyses*

No formal statistical analyses will be performed, although descriptive summaries for continuous data and for categorical data will be provided in accordance with Section 5.3 if other not stated. Complete listings of all patient safety evaluations will be provided to support each summary table.

All presentations will be based on the safety analysis set.

5.7.1 *Adverse Events*

Adverse Events (AEs) will be coded by system organ class (SOC), preferred term (PT) and Verbatim name using MedDRA Version 20.0

All AEs will be listed whereas the treatment emergent AEs (TEAEs), i.e. any AE with onset or worsening on or after the first dose of any IMP and within 30 days after the last dose of IMP, will be summarized as follows. The number of TEAEs, as well as the number and percentage of patients reporting any TEAE will be summarised for Cycle 1, subsequent cycles and Safety follow-up by cohort. Separate summary tables will be produced for the following:

1. TEAEs related to IMP by Verbatim names
2. TEAEs related to IMP by SOC and PT
3. TEAEs not related to IMP by Verbatim name
4. TEAEs not related to IMP by SOC and PT
5. Serious Adverse Events (SAEs) by Verbatim name
6. SAEs by SOC and PT.
7. TEAEs related to IMP by AE grade
8. TEAEs not related to IMP by AE grade

AEs leading to withdrawals or death will be presented by cohort.

All percentages will be based on the number of patients in the safety set.

5.7.2 *Clinical Laboratory Tests*

All laboratory parameters for individual patients will be listed and patients with abnormal values (out of normal range reported by the laboratory) and with clinically significant abnormalities (according to the Investigator's criteria) will be flagged.

Clinical Laboratory Tests (hematology, clinical chemistry, immunology, serology, urinalysis, pregnancy testing and histology) will be summarized regarding observed values, change from baseline and abnormal findings in accordance with Section 5.3 by cancer cohort and in total over cohorts. In addition, the categorization of the observed values into 'low', 'normal' and 'high' will be summarized in max/min shift from baseline tables by cohort and in total over cohorts. There will be two variants of each shift table, one where the max/min is taken over the samples taken after the first dose but before the 2nd dose and one where the max/min is taken over all samples taken after the first dose.

5.7.3 *Physical Examination*

Physical examination will be presented as the number and percentage of patients with normal, abnormal not clinically significant, abnormal clinically significant result over time by Body System and cancer cohort.

Findings that are present during screening and prior to drug administration will be included under Medical History. Significant findings made after drug administration that meet the definition of an AE will be reported under the AE section.

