2.2.2 Secondary Objectives

1. To assess the safety and tolerability of the combination of pembrolizumab and birinapant; Overall and in the defined tumor types, colorectal cancer, ovarian cancer and cervical cancer.

2. To assess clinical activity of the combination of pembrolizumab and birinapant in the defined tumor types by effects on tumor response, including CBR, time to response and duration of response, assessed by RECIST 1.1
3. To assess clinical activity of the combination of pembrolizumab and birinapant in the defined tumor types by effect on overall survival
4. To assess clinical activity of the combination of pembrolizumab and birinapant in the defined tumor types by effect on progression free survival.

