3.4 Study Endpoints

3.4.1 Study Endpoints: Dose Escalation Phase

3.4.1.1 Primary Endpoint

Safety and tolerability will be assessed by monitoring:

- Incidence and severity of adverse events (AEs) experienced by patients receiving birinapant in combination with pembrolizumab.
- Incidence and magnitude of clinically significant changes in clinical laboratory parameters experienced by patients receiving birinapant and pembrolizumab, or overall pattern of shifts by treatment group in individual laboratory values suggestive of possible trends, but not necessarily establishing, clinical abnormality.
- Incidence and severity of clinically significant adverse findings in vital signs, electrocardiogram (ECGs), and other physical examination parameters among patients receiving birinapant and pembrolizumab.

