3.4.2 Study Endpoints; Dose Expansion Phase

3.4.2.1 Primary Endpoint

The primary endpoint in each of the cohorts is as follows:

1. The overall response assessed through RECIST v.1.1 until response or progression in colorectal cancer
2. The overall response assessed through RECIST v1.1 until response or progression in ovarian cancer
3. The overall response assessed through RECIST v1.1 until response or progression in cervical cancer
4. Safety and tolerability in the cohort with various solid tumor types will be assessed by monitoring:
 - Incidence and severity of adverse events (AEs) experienced by patients receiving birinapant in combination with pembrolizumab.
 - Incidence and magnitude of clinically significant changes in clinical laboratory parameters experienced by patients receiving birinapant and pembrolizumab, or overall pattern of shifts by treatment group in individual laboratory values suggestive of possible trends, but not necessarily establishing, clinical abnormality.
 - Incidence and severity of clinically significant adverse findings in vital signs, electrocardiogram (ECGs), and other physical examination parameters among patients receiving birinapant and pembrolizumab.

Measures of tumor response will be evaluated using RECIST v1.1 until response or progression and will be subsequently analyzed through iRECIST as an exploratory endpoint (see below).

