AEs will be reported in accordance with the NCI CTCAE v4.03, using a recognized medical term or diagnosis that accurately reflects the event. AEs will be assessed by the Investigator for severity and relationship to investigational product (birinapant/pembrolizumab), for other possible etiologies, and whether the event meets criteria as an SAE and therefore requires immediate notification to the Sponsor. If an AE has not resolved at the end of the study reporting period, it will be documented as ongoing. If an AE evolves into a condition that becomes “serious,” it will be reported as an SAE.

For hematological toxicity fluctuations, record the highest grade during the cycle on the patient’s eCRF.

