12.6 Analysis of Safety Data

The safety and tolerability of pembrolizumab and birinapant will be based on results of DLT incidence, reported SAEs, AEs, vital sign measurements, physical examinations, clinical laboratory information, ECOG performance status, and concomitant medications. Exposure to study drug and reasons for discontinuation will be tabulated. These data will

be summarized descriptively for the dose escalation phase and for the dose expansion phase of the protocol separately for the ITT population. Safety data will be summarized descriptively by cohort and also summarized descriptively over cohorts within each of the two phases of the protocol.

For parameters measured over time, data and changes from baseline will be summarized for each time point. Adverse events will be coded using the current *Medical Dictionary for Regulatory Activities* (MedDRA) classification system, and will be summarized by system organ class and preferred term.

Additional safety analyses may be determined in order to most clearly describe toxicity rates and to further define the safety profile of pembrolizumab and birinapant.

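### SAP 5.7.1 splits its TEAE tables by causality and period, so they only bound the any-cause incidence and severity named in the primary safety endpoint; lab shift tables miss worsening from a raised baseline

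*SAP*

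**What the plan says.** **Endpoint.** Protocol 3.4.1.1 makes the first component of the escalation-phase primary endpoint "Incidence and severity of adverse events (AEs) experienced by patients receiving birinapant in combination with pembrolizumab". Protocol 3.4.2.1 repeats that wording for the fourth expansion cohort: "Safety and tolerability in the cohort with various solid tumor types will be assessed by monitoring". Neither section limits the events to those judged drug-related. The second component in both sections concerns the incidence and magnitude of clinically significant laboratory changes, or the overall pattern of shifts.

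**Protocol analysis section.** Protocol 12.6 asks for adverse events by system organ class (SOC) and preferred term (PT), and adds: "Safety data will be summarized descriptively by cohort and also summarized descriptively over cohorts within each of the two phases of the protocol". The first secondary objective of the expansion phase (Protocol 2.2.2) is likewise framed as "Overall and in the defined tumor types, colorectal cancer, ovarian cancer and cervical cancer".

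**SAP 5.7.1.** The any-TEAE line reads "number and percentage of patients reporting any TEAE will be summarised for Cycle 1, subsequent cycles and Safety follow-up by cohort". Eight tables follow. Verbatim-term and SOC/PT tables are given for related and for not-related events (for example "TEAEs related to IMP by SOC and PT"). The grade tables have the same split (for example "TEAEs not related to IMP by AE grade"). The two tables of serious events carry no causality split, nor do the adverse events leading to withdrawal or death, which are presented by cohort. All adverse events are listed.

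**SAP 5.7.2.** Laboratory data are summarised as observed values, change from baseline and abnormal findings. Shift tables, in categories of low, normal and high, are added to these.

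**The concern.** The endpoint asks how many patients had an event and how severe it was. The planned tables answer a different question: how many patients had an episode judged related, and how many had one judged not related. Under Protocol 8.1.1 the investigator judges causality for each event, so one patient can have a related and a not-related episode of the same term. Event counts then add across the two tables, but patient counts do not. The any-TEAE count has the same difficulty across its three periods.

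In a single-arm trial of two drugs, relatedness is a judgement with no control group to check it. Protocol 8.1.3 has four relationship categories, and SAP 5.7.1 does not say which of them count as related. The any-cause count is the one figure that depends on neither, and no table commits to it by term or by grade.

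Severity has a further gap. The grade tables do not say whether a patient is counted once at maximum grade, and they do not cross grade with term.

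The laboratory point is narrower. A three-category shift table cannot register worsening in a patient who starts in the high category, and entry permits that for AST and ALT.

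**Working it through.** The plan states no figure to reproduce. The check sets texts side by side and then bounds what the planned tables can recover.

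**1. What SAP 5.7.1 gives without a causality split**

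- Any TEAE: yes, but by period and cohort only.
- Serious events by verbatim term and by SOC/PT: yes.
- Events leading to withdrawal or death: yes.
- TEAEs by verbatim term or SOC/PT: no.
- TEAEs by grade: no.

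**2. Patients with a given term from any cause**

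Let *a* patients of *n* have the term as related and *b* have it as not related. The any-cause number lies between max(*a*, *b*), when the smaller group sits wholly inside the larger, and min(*n*, *a* + *b*), when no patient is in both. If *a* + *b* ≤ *n*, the width of this range is min(*a*, *b*). It vanishes only when one count is zero. The documents give no event counts, so those below are assumed. The cohort size of 30 and the maximum of 6 per dose level come from the protocol.

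| *n* | related, not related | lower | upper |
|---|---|---|---|
| 30 | 3, 3 | 3 (10.0%) | 6 (20.0%) |
| 30 | 6, 9 | 9 (30.0%) | 15 (50.0%) |
| 30 | 12, 12 | 12 (40.0%) | 24 (80.0%) |
| 6 | 2, 3 | 3 (50.0%) | 5 (83.3%) |

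The same bounds hold for patients reaching a given grade or worse, if *a* and *b* are read as the patient counts at that level in the two grade tables.

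**3. Patients with any TEAE over the whole period**

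The lower bound is the largest period count. The upper bound is the sum of the three, capped at *n*. With assumed counts in 30 patients:

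- 15, 20 and 10: lower 20 (66.7%); the sum is 45, so upper 30 (100%).
- 8, 10 and 4: lower 10 (33.3%); upper 22 (73.3%).

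**4. Total within phase**

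SAP 5.3 specifies a column for cohort and makes pooling across the two phases optional. Medical history (5.5.4), laboratory tests (5.7.2) and vital signs (5.7.4) are each given in total over cohorts; adverse events are not. Cohorts are disjoint, so a total follows by addition from any cohort counts that are themselves exact.

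**5. Laboratory shifts**

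Protocol Table 4 admits AST and ALT up to 2.5×ULN, or 5×ULN with liver metastases. Example values:

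- 2.5 to 10×ULN: a rise of 10/2.5 = 4-fold, shown as high to high.
- 4.9 to 19×ULN (liver metastases): 19/4.9 = 3.9-fold, shown as high to high.
- 1.0 to 1.1×ULN: shown as normal to high.

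If 10%, 20% or 40% of 30 patients enter with AST above ULN (an assumed range), then 3, 6 or 12 patients cannot show an upward AST shift. Protocol Table 6 separates Grade 2 AST/ALT elevation from Grade 3 or 4 when deciding on pembrolizumab; the shift table puts all of these in one category.

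**The case against.** The strongest reply is that this concerns table layout, not data. All adverse events are listed, and in a cohort of 30 or a dose level of 6 the exact counts can be read off. SAP section 1 places the mock-up tables in a separate document, not available here, which may already contain a maximum-grade table, a whole-period row and a total column. Escalation runs on dose-limiting toxicities, the monitoring committee reviews combined toxicities itself, and no safety inference is planned. All of that stands, and it limits the weight of the point. It does not supply the missing commitment: a hand count from listings is not a pre-specified summary of a primary endpoint.

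Several stronger readings are tempting, and the documents do not support them.

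- *The SAP has no any-cause safety output.* It has: any TEAE by period, serious events, and events leading to withdrawal or death.
- *Splitting by causality contradicts Protocol 12.6.* That section asks for SOC/PT summaries but not for one undivided table, and the two SOC/PT tables together cover every TEAE.
- *The absent total loses information.* Counts add across cohorts. It is an omission against Protocol 12.6, not listed among the changes in SAP 5.9, and minor.
- *Laboratory worsening is hidden.* Only the shift table has the blind spot. Observed values, changes from baseline and the minimum and maximum over later cycles (SAP 5.3) show part of it, and an abnormal value reported as an adverse event is graded.
- *Amylase and lipase share the raised-baseline problem.* Inclusion criterion 7 requires both to be below ULN.

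**Conclusion.** The concern holds as a gap in what the SAP text commits to. Followed as written, SAP 5.7.1 yields bounds, not counts, for any-cause incidence by term, for any-cause severity, and for patients with any TEAE over the whole period. The first two are what the primary safety endpoint names for the escalation phase and the various-tumors cohort.

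The size depends on how often patients fall into both causality tables or into several periods, which cannot be known in advance. Under the assumed counts the range runs from 10 percentage points (3 and 3 of 30) to 40 (12 and 12 of 30). These are extreme bounds and not expected errors; for a term with events on one side only, the range is zero.

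The laboratory part holds only for analytes that may be abnormal at entry, chiefly AST and ALT, and only for the shift table. The change is worth making because it is cheap and bears on a primary endpoint. A reader might infer that safety data are lost or that dosing or stopping decisions are compromised; neither follows.

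**What to change.** **SAP 5.7.1.** Add, as the main adverse-event table, TEAEs of any causality by SOC and PT and by maximum CTCAE grade. Count each patient once per row over the whole TEAE period, and include a row for any TEAE. Show it by dose level or cohort, with a total within each phase as Protocol 12.6 asks. Keep the existing causality and period tables as supportive.

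**SAP 5.7.2.** For CTCAE-gradable analytes that may be abnormal at entry, AST and ALT above all, replace the low/normal/high categories in the shift tables with CTCAE v4.03 grade, from baseline to worst value after first dose.

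**Cost.** SAP wording and table programming, using grades, causality and chemistry already collected. No added visits, samples or patients.
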